4.3 Rationale for Design of Trial

This study is designed as an acute administration, proof of concept study to determine whether administration of intranasal insulin results in increased delivery to the CNS as evidenced by increased CSF insulin levels relative to placebo.

4.4 Rationale for Biofluids

The CSF biomarkers insulin, A β 42, A β 40 and total tau will be measured. Plasma biomarkers including A β 42, and A β 40 will be also assessed. Plasma and CSF samples obtained in this study will be banked so that other putative biomarkers may be measured by qualified investigators in the future given adequate rationale and feasibility.

Several previous studies suggest that response to insulin may differ according to APOE genotype. In dose response studies that acutely elevated insulin through intravenous or intranasal administration, the greatest cognitive benefit was observed for adults with AD who were not ϵ 4 carriers (Reger, Watson et al. 2008). The current study will examine ϵ 4 carriage as a treatment response predictor.

5.0 STUDY OVERVIEW

The study will consist of a single site, randomized, double-blind trial comparing the acute effects of INI (20 International Units) or placebo delivered with the ViaNase device on CSF insulin levels, AD biomarkers and memory. At study entry, participants will be randomized to receive either an acute dose of insulin or of placebo first, and the other substance on a second visit. Participants who are cognitively normal or who have aMCI (n=30) will be enrolled. The primary outcome measure will consist of CSF insulin levels. Secondary measures will include a memory test and CSF biomarker levels.

5.1 Study Population

A total of 30 adults who are cognitively normal or diagnosed with aMCI will be enrolled in this trial. We expect to enroll approximately 50% of participants from each group. To determine eligibility, all participants will undergo cognitive assessment, physical and neurological examination, ECG, clinical/safety laboratory assessment, and interviews of the participant and study partner conducted by the investigators and staff of the Clinical Core of the Wake Forest Alzheimer's Disease Research Center (ADRC).

5.2 Diagnosis Criteria

Diagnoses will be assigned by consensus of investigators from the Clinical Core of the Wake Forest ADRC using criteria specified by the NIA and Alzheimer's Association MCI workgroup (Petersen, Doody et al. 2001, Albert, Dekosky et al. 2011).

Criteria for cognitively normal adults:

- a) No evidence of significant cognitive impairment on objective testing
- b) Clinical Dementia Rating Scores of 0

Diagnosis of aMCI requires:

- a) Evidence of a decline in episodic memory (memory scores below age and education-based norms)
- b) General preservation of independence in functional abilities
- c) Absence of dementia

5.3 Inclusion Criteria

The following inclusion criteria* will be used:

1. Age 55 to 85 (inclusive)
2. Fluent in English
3. Cognitively normal or diagnosis of aMCI by criteria described above
4. MMSE \geq 24 at screening. Approval for exceptions can be requested to the Project Director for minority or low education participants
5. CDR 0-0.5 (inclusive) at screening
6. Stable medical condition for 3 months prior to screening visit
7. Stable medications for 4 weeks prior to the screening and study visits
8. Clinical laboratory values must be within normal limits or, if abnormal, must be judged to be clinically insignificant by the study physician

*Exceptions to these criteria may be considered on a case-by-case basis at the discretion of the Project Director and study physician, and must be approved in advance by the IRB.

5.4 Exclusion Criteria

The following exclusion criteria* will be used:

1. A diagnosis of dementia
2. History of a clinically significant stroke
3. Current evidence or history in past two years of epilepsy, focal brain lesion, head injury with loss of consciousness or DSM IV criteria for any major psychiatric disorder including psychosis, major depression, bipolar disorder, alcohol or substance abuse
4. Sensory impairment that would preclude the participant from participating in or cooperating with the protocol
5. Diabetes (type I or type II) requiring pharmacologic treatment (including both insulin dependent and non-insulin dependent diabetes mellitus)
6. Current or past use of insulin or any other anti-diabetic medication within 5 years of Screening visit.
7. Evidence of any significant clinical disorder or laboratory finding including clinically significant or unstable hematologic, hepatic, cardiovascular, pulmonary, gastrointestinal, endocrine,

metabolic, renal or other systemic disease or laboratory abnormality

8. Active neoplastic disease, history of cancer five years prior to screening (history of skin melanoma or stable prostate cancer are not exclusionary)
9. History of seizure within past five years
10. Pregnancy or possible pregnancy. Participant is not pregnant, lactating, or of childbearing potential (i.e. women must be two years post-menopausal or surgically sterile)
11. Contraindications to LP: prior lumbosacral spine surgery, severe degenerative joint disease or deformity of the spine, platelets <100,000 or history of a bleeding disorder
12. Use of anticoagulants warfarin (Coumadin) and dabigatran (Pradaxa) (due to LP requirement)
13. Residence in a skilled nursing facility at screening
14. Use of an investigational agent within two months of screening visit
15. Regular use of narcotics, anticonvulsants, medications with significant anticholinergic activity, antiparkinsonian medications, or any other exclusionary medications

*Exceptions to these criteria may be considered on a case-by-case basis at the discretion of the Project Director and Study Physician, and must be approved in advance by the IRB.

5.5 Recruitment and Retention Strategies

Recruitment will occur primarily from the Clinical Core of the Wake Forest ADRC. Some participants may also be identified from community recruitment efforts.

6.0 STUDY TIMELINE

The approximate timeline for this twenty-one-month study is projected as follows: 1) approximately one months for study startup activities; 2) study visits and data collection will occur over an eighteen-month period; 3) CSF and blood analyses, data analyses and study dissemination will occur over the final 2 months.

7.0 DESCRIPTION OF STUDY VISITS

The "Schedule of Study Procedures and Assessments" in Table 4 provides an overview of study visit activities. The primary and secondary outcome measure will be measured at both study visits. Genotyping will occur at Screening for participants who have not previously received APOE genotypes through the ADRC.

7.1 Screening (Visit 1)

The purpose of this visit is to determine study eligibility. Potential participants must sign an informed consent form and HIPAA Authorization prior to administration of any study-related procedures. After consent is obtained, participants will be given the MMSE, the CDR and Story Recall to determine study eligibility. Screening may be waived for participants who have received evaluations from the ADRC within the past 12 months.

In addition, information regarding demographics, concurrent medications, medical history and adverse events will be gathered from the participant. Vital signs, height and weight will be measured. A brief physical and neurological examination (which include a nasal examination) and a standard 12-lead resting ECG will be performed. The ECG report will be reviewed, signed, and dated by the investigator or a medically qualified staff member as delegated by the Principal Investigator. Those with clinically significant ECG findings will be referred for follow-up as deemed appropriate by the investigator. These procedures may be waived for participants who have received evaluations from the ADRC within the past 12-months.

Blood will be drawn for routine clinical laboratory evaluations. If values are outside of the laboratory's normal range and determined clinically significant by the investigator, lab tests may need to be repeated and may be considered exclusionary for participation in the study. Blood samples will also be collected for ApoE genotyping and optional DNA storage.

7.2 Baseline (Visit 2)

Results from all screening procedures must be reviewed and all inclusion/exclusion criteria must be met prior to proceeding to baseline. For participants whose screening visit was waived because they had received ADRC evaluations within the past 12-months will sign an informed consent form and HIPAA Authorization prior to administration of any study-related procedures.

According to the randomization schedule, the participant will receive a dose of 20 International Units insulin or placebo administered with the ViaNase device. They will then begin preparations for the lumbar puncture. After preparation, the immediate recall section of the AVLT will be administered. Blood for plasma biomarkers will then be collected immediately before and after participants undergo the lumbar puncture. Fasting plasma insulin, glucose, A β 40 and A β 42 will be measured. Additional plasma and serum will be collected and banked.

Lumbar puncture will then be performed in the morning after a minimum 8-hour overnight fast. CSF samples will be used to measure levels of insulin, A β 42, A β 40, total tau, and phospho-tau181. Additionally, CSF sample will be banked for future exploratory analysis. CSF will be collected and immediately frozen upright on dry ice. Site staff will call the participant within 24 hours from the lumbar puncture procedure to inquire about the participant's well-being and possible adverse events. Following the lumbar puncture, the delayed recall section of the AVLT will be administered. Participants will then receive a snack and instructions about post-lumbar puncture care.

7.3 Visit 3

Visit 3 will be scheduled within 2 to 6 weeks following Visit 1. Vital signs and weight will be obtained, a nasal examination will be conducted, adverse events and concurrent medications will be recorded. Procedures will follow the schedule outlined for Visit 1, except that the alternate compound (either saline or 20 International Units insulin) will be administered.

8.0 STUDY-SPECIFIC PROCEDURES

8.1 Memory Evaluation Instruments Administered to the Participant

Objective tests of cognitive function will include MMSE, Story Recall, and the Rey Auditory Verbal Learning Test.

8.2 Clinical and Functional Evaluations

8.2.1 Clinical Dementia Rating Scale – Sum of Boxes (CDR-SB)

The CDR (Hughes, Berg et al. 1982, Morris 1993) is a clinical scale that rates the severity of dementia as absent, questionable, mild, moderate, or severe (CDR score of 0, 0.5, 1, 2, or 3, respectively). The score is based on interviews with the participant and study partner, using a structured interview that assesses six domains: memory, orientation, judgment and problem solving, community affairs, home and hobbies, and personal care.

At Screening the CDR global score will be used for eligibility purposes. For all other administrations, the 6 domain scores will be summed to get the Sum of Boxes (SB) score. Training on the use of the CDR will be conducted to standardize its administration across sites. The CDR online training tool resides on the Washington University, St. Louis website, with oversight provided by [name] (Morris, Ernesto et al. 1997).

9.0 STUDY METHODS

9.1 Safety Assessments

At each study visit, all participants will undergo a nasal examination and any occurrence of adverse events will be reviewed and documented; concomitant medications will be recorded as well. In addition, 24 hours after the Lumbar Puncture, each study participant, or a person designated to speak for them will be contacted by phone to confirm the participant's well being and queried about any new adverse events. All adverse events will be reported to the Wake Forest DSMB. Safety reports will be prepared by study team and submitted to the DSMB for periodic review.

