10.0 BIOMARKER STUDIES

10.1 CSF

All CSF samples will be collected in the morning before breakfast and after an overnight fast. Participants who are taking anticoagulants, warfarin (Coumadin) and dabigatran (Pradaxa) should not be screened for this trial, as these are prohibited medications. Based on clinician judgment and depending on the clinical indication, it may be suitable to discontinue participants from their anti-platelet agent (e.g., aspirin, Plavix, NSAIDs) for 5-7 days prior to lumbar puncture and until at least 24 hours after lumbar puncture. It is not required that participants be discontinued from their anti-platelet agent in order to screen and enroll in the study.

A minimal total volume of CSF (25 ml) will be required for this study. To clear any blood from minor trauma associated with needle insertion, the first 1-2 mL of CSF are discarded (or more if needed). Collected CSF is aliquoted into sterile microtubes. Approximately 2ml of CSF or volume per local laboratory requirements will be sent at ambient temperature to the CRU laboratory for protein, glucose and cell count. The remaining CSF will be immediately frozen upright on dry ice for at least 20 minutes then stored at -70 until analysis.

CSF samples will be used to measure levels of insulin, A β 42, A β 40, total tau, and phospho-tau181. Assays will be performed by the Wake Forest ADRC Biomarker Service. CSF samples will also be frozen and stored for future analysis of putative biomarkers.

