12.3 Lumbar Puncture

Lumbar puncture may be associated with pain during the performance of the procedure. This is usually temporary and confined to the lower back. Headache may occur in about 5% of elderly people who undergo lumbar puncture. Less commonly, in about 1-4% of participants, a persistent low-pressure headache may develop, probably due to leakage of CSF. Lower rates of post-LP headache have been noted in elderly patients, and when atraumatic (Sprotte) needles are used. If a post-LP headache persists it may need additional treatment, e.g. with fluids and analgesics. Uncommonly a blood patch (injection of some of the participant's blood to patch the CSF leak) may be needed. Potential but rare risks of lumbar puncture include infection, damage to nerves in the back, and bleeding into the CSF space. The risk of these is much less than 1%.

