22.0 TABLE 4: SCHEDULE OF PROCEDURES AND ASSESSMENTS

Visit #	1	2	3
Visit Name	Screen	Study 1	Study 2
Informed Consent	X		
Demographics	X		
Medical History	X		
Concomitant Meds	X	X	X
Nasal Exam	X	X	X
Physical and Neurological Exam	X		
Vital Signs	X	X	X
Height	X		
Weight	X		
ECG	X		
Story Recall	X		
MMSE	X		
CDR	X		
Adverse Events	X	X	X
Blood Draw	X		
- Clinical Labs	X		
- ApoE Genotyping DNA Banking ¹	X		
- Biomarkers Plasma Serum Sample Banking		X	X
LP		X	X
- CSF Biomarkers Banking ²		X	X
- post-procedure safety telephone check		X	X
Auditory Verbal Learning Test		X	X

¹DNA banking is optional

²CSF banking is optional

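### After the second lumbar puncture the only scheduled safety contact is one phone call about a day later, so non-serious events that begin after it may go uncollected

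*Combined protocol and SAP*

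**What the plan says.** Three places set the safety contacts around each LP.

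- **Section 9.1** requires in-person review at visits: "At each study visit, all participants will undergo a nasal examination and any occurrence of adverse events will be reviewed and documented". It then adds the telephone contact: "24 hours after the Lumbar Puncture, each study participant, or a person designated to speak for them will be contacted by phone".
- **Section 7.2**, on the first dosing visit, times the call differently: "Site staff will call the participant within 24 hours from the lumbar puncture procedure".
- **Table 4 (Section 22.0)** ticks the "post-procedure safety telephone check" for Visits 2 and 3. Visit 3 is the last column; no later call or visit appears.

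Section 7.3 describes the second dosing visit: "Vital signs and weight will be obtained, a nasal examination will be conducted, adverse events and concurrent medications will be recorded". It fixes the timing as follows: "Visit 3 will be scheduled within 2 to 6 weeks following Visit 1". In Section 7.1 and Table 4, Visit 1 is Screening; the first dose and LP are at Visit 2.

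Among the LP risks, Section 12.3 gives headache in about 5% and adds: "Less commonly, in about 1-4% of participants, a persistent low-pressure headache may develop, probably due to leakage of CSF".

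**The concern.** The two treatment periods are not observed alike. An event that starts some days after the first LP is asked about at Visit 3. The same event after the second LP meets no scheduled question, because the call has already been made. Anyone affected has to contact the site unprompted.

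Two things are at stake. The first is completeness: this is a two-LP study in older adults, and its own risk section names a complication that lasts. The second is comparability. Section 19.4 lets the monitoring board recommend stopping on a treatment difference in AEs, yet the documents define no common AE window after each dose. A plain count by treatment would mix exposures followed until the next visit with exposures followed for about a day.

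**Working it through.** The plan gives no expected AE count to reproduce, and Section 11.1 says that no power calculation was done. The check is therefore a comparison of passages, followed by arithmetic for scale.

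**1. Scheduled safety contacts after each dose and LP**

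| | After Visit 2 | After Visit 3 |
|---|---|---|
| Telephone check (7.2, 9.1, Table 4) | yes | yes |
| Later AE review | yes, at Visit 3 | none |
| Nasal examination at a later visit | yes, at Visit 3 | none |

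**2. Length of the first window.** If Visit 1 in Section 7.3 means the first dosing visit, the scheduled AE window is 14 to 42 days after the first LP, against about 1 day after the second. That reading is plausible, because 7.3 says Visit 3 repeats Visit 1 with the other compound, and no compound is given at Screening. As written, though, the interval runs from Screening and no minimum gap between dosing visits is fixed. The first window is longer under either reading, but the 14 to 42 days depends on which one applies.

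**3. What other sections catch.** Section 15.2 obliges the investigator to follow known AEs until they subside, are medically stable or the participant is unavailable. Section 16.2 covers serious events at any time after consent. Neither creates a contact that would reveal a new non-serious event.

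**4. Scale after the last LP.** Inputs: 30 participants (5.1) and a persistent headache rate of 1% to 4% (12.3). Assumptions: all 30 reach Visit 3 and events are independent. Section 12.3 words the rate per participant, so both readings are shown.

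- Rate per LP: 30 × 0.01 = 0.3 and 30 × 0.04 = 1.2 expected. Chance that at least one occurs: 1 − 0.99^30 = 0.26 and 1 − 0.96^30 = 0.71.
- Rate per participant, split evenly over two LPs: 30 × 0.01 / 2 = 0.15 and 30 × 0.04 / 2 = 0.6 expected. Chance that at least one occurs: 1 − 0.995^30 = 0.14 and 1 − 0.98^30 = 0.45.

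The number missed is the expected number × the share starting after the call × the share not volunteered. The documents give neither share, and each can lie anywhere from 0 to 1. The number missed therefore runs from 0 up to 0.3 to 1.2, or up to 0.15 to 0.6.

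**5. Effect on the treatment comparison.** Section 14.3 randomises order 1:1. With 15 participants per sequence, each treatment has 15 exposures in the long window and 15 in the short one. Taking step 2's first reading, the mean window is (14 + 1)/2 = 7.5 days at the shortest gap and (42 + 1)/2 = 21.5 days at the longest, the same for insulin and saline.

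**The case against.** The strongest reply is that the protocol already has a working safety net. The call asks about new AEs, known AEs are followed to resolution or stability, serious events have no per-participant cut-off, and participants leave with post-LP care instructions. This is a 30-person, two-dose proof of concept, and Section 11 plans no AE analysis by treatment. Much of that stands, and it rules out several stronger readings that a reader might infer:

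- **That persistent events go uncollected.** A headache present at the call must be followed under 15.2, which is how its persistence would be established.
- **That 26% to 71% is the chance of missing a persistent headache.** It is the chance that one occurs, and only on the per-LP reading.
- **That the comparison is biased for or against insulin.** The 1:1 order balances the windows on average. Dropout or an uneven split could disturb that balance, but the documents point to no direction.
- **That the nares are never examined after the second dose.** Section 7.3 lists the examination early in the visit, but neither it nor 9.1 or 9.2 says whether it comes before or after dosing.
- **That a call soon after the LP is enough.** It would satisfy 7.2 but not 9.1; this is a conflict in wording.

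The reply does not supply a scheduled contact after the last call. For a non-serious event that begins later, capture depends on the participant reporting it.

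**Conclusion.** The point holds in a limited form. A study run exactly to plan has no scheduled way to learn of a non-serious LP or nasal event that begins after the Visit 3 call, while the equivalent event after Visit 2 is asked about at Visit 3. Ascertainment is longer for the first treatment than for the second. The consequence is some under-counting and an imbalance between periods.

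For persistent headache, the amount missed could be nothing and is at most 0.3 to 1.2 expected cases per LP-based rate, or 0.15 to 0.6 per participant-based rate. This rests on all 30 participants reaching Visit 3 and on 12.3's rates applying here. The text between Sections 12.4 and 14.0 was not available to check, so the statement that nothing follows the call rests on Table 4 and Sections 7 and 9. This is an inexpensive improvement in safety capture and does not threaten the primary aim.

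**What to change.** 1. Reconcile the call time in Sections 7.2 and 9.1, and state which visit Section 7.3 means when it counts the interval to Visit 3.
2. Repeat the same AE call script on one common later day after both LPs, no later than the shortest gap between dosing visits once 7.3 is settled. Add the call to Table 4 for Visits 2 and 3.
3. Define the time from each dose to that call as the AE collection period, say when collection ends after Visit 3, and add to Section 11 a table of AEs by treatment within that window.

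The cost is up to 30 × 2 = 60 short calls by existing staff and the edits above. The downside is that participation ends slightly later.

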9.2 Physical and Neurological Examination

A brief physical examination will be performed by a medically qualified professional at the screening visit. A review of the major body systems will be performed for example: skin, head/ears/eyes/nose/throat (HEENT), cardiovascular, pulmonary, abdomen, musculoskeletal, neurological, and gastrointestinal. Assessments of height (Screening visit only), weight, and vital signs (systolic and diastolic blood pressure, pulse, temperature, and respiration) are included. Neurological examination will include an assessment of cranial nerves, strength, coordination, reflexes, sensation, tremor and gait at every study visit. A nasal examination will also be performed. The examination will assess irritation or other abnormalities of the nares.

9.3 Electrocardiogram (ECG)

A standard 12-lead resting ECG will be performed at Screening visit. The ECG report will be reviewed, signed, and dated by the investigator. Those with clinically significant ECG findings will be referred for follow-up as deemed appropriate by the investigator and may be excluded from the study.

